## **SYNOPSIS**

The “Ascorbic Acid, Corticosteroids, and Thiamine in Sepsis (ACTS)” trial is a multi-center, double-blind, randomized clinical trial that aims to determine the impact of Vitamin C, Hydrocortisone, and Vitamin B1 vs. Placebo on organ injury and mortality on participants with sepsis and septic shock. The trial will be conducted in accordance with all applicable national and international laws, regulations, and guidelines. The trial and this protocol is developed in accordance with the International Conference on Harmonization (ICH) guidelines and the Standard Protocol Items: Recommendations for Interventional Trials (SPIRIT) statement. The principal investigator wrote the protocol with input from the steering committee. Any substantial changes or amendments to the protocol will be clearly documented and communicated to all relevant parties.

## TRIAL OVERVIEW

**Title** Vitamin C, Hydrocortisone, and Vitamin B1 in Sepsis and Septic Shock – A Randomized, Double-Blind, Placebo-Controlled Trial (The ACTS Trial)

Clinical Trials Number	NCT03389555
Sources of monetary or material support	Open Philanthropy Project ( https://www.openphilanthropy.org/ )
Study Sites	12-sites in the United States
Condition studied	Sepsis and septic shock
Interventions	Vitamin C (1.5g every 6 hours x 4-days), hydrocortisone (50mg every 6 hours x 4-days), and Vitamin B1 (100mg every 6 hours x 4-days)
Comparator	Placebo
Inclusion criteria	

• Adult participant (age ≥ 18 years)

• Suspected (cultures drawn and antibiotic given) or confirmed (via culture results) infection

• Receiving vasopressor (norepinephrine, phenylephrine, epinephrine, dopamine, vasopressin, or angiotensin II)

Exclusion criteria	

• Member of a protected population (pregnant, prisoner)

• Known history of kidney stones within the past 1 year

• End stage renal disease (ESRD) requiring dialysis

• Known history of G6PD deficiency

• Known history of Hemochromatosis

• Comfort Measures Only status

• Anticipated death within 24-hours despite maximal therapy (as determined by the enrolling physician)

• Receiving supplemental vitamin B1 in a dose greater than that contained in a multivitamin (<2mg)

• Clinical indication for steroids (e.g. chronic use) as determined by the clinical team providing this drug

• Clinical indication for ascorbic acid supplementation in any form

• Clinical indication for vitamin B1 as determined by the clinical team providing this drug

• Known allergy to vitamin C, hydrocortisone, or vitamin B1

Study type	Interventional Allocation: Randomized (1:1) Intervention model: Parallel group Masking: Double-blind
Target sample size	200 Participants (100/arm)
Primary outcome	Change in the Sequential Organ Failure Assessment (SOFA) score between enrollment and 72-hours
Key secondary outcomes	Incidence of renal failure during index ICU stay 30-day mortality

### **Conflicts of interest**

The members of the steering committee have no financial conflicts of interest related to the current trial.

## **1. BACKGROUND AND SIGNIFICANCE**

### **1.1 Scope of the Problem**

The worldwide incidence of sepsis has been estimated at more than 23 million cases and sepsis contributes to more than a third of all hospital deaths in the United States. Mortality for those in septic shock with elevated lactate is more than 40%. In addition to high short-term mortality, sepsis is associated with significant post-discharge morbidity and mortality. The economic burden for participants suffering from sepsis is staggering with an estimated yearly financial burden of \$17 billion. Treatments are generally limited to antibiotics and intravenous fluids while providing support to maintain organ function.

### **1.2 Existing Interventions**

To date, numerous interventions have been tested for participants with sepsis and septic shock with limited, if any, success. Recently, three large studies found no benefit from early goal directed therapy over usual care in emergency department participants with sepsis. Other recent studies focusing on hemodynamics, fluid therapy, and transfusions have also failed to show a significant benefit in this participant population. Previous studies focusing on immunomodulatory therapies or drotrecogin alfa have likewise shown disappointing results.

### **1.3 The combination of vitamin C, hydrocortisone, and vitamin B1 may improve outcomes**

In a before-and-after study exploring the effects of the combination of vitamin C, hydrocortisone, and vitamin B1 in a cohort of participants with sepsis and septic shock, Marik et. al. found a remarkable improvement in time to shock reversal ( $18.3 \pm 9.8$  hours vs.  $54.9 \pm 28.4$  hours), organ injury ( $\Delta$ SOFA  $4.8 \pm 2.4$  vs.  $0.9 \pm 2.7$ ), and mortality (8.5% vs. 40.4%) following implementation of the drug 'cocktail' as compared to before implementation even after adjusting for potential confounders. This study joins other promising trials of individual elements of this drug combination. In a trial of vitamin B1 in septic shock, there was a substantial reduction in mortality and organ injury (particularly kidney injury) in those with vitamin B1 deficiency and septic shock who were given vitamin B1 as compared to placebo. In addition, several studies of vitamin C alone have shown promise in critically ill populations and a recent meta-analysis of corticosteroids in sepsis suggests potential benefit.

### **1.4 Physiologic Rationale**

The combination of vitamin C, hydrocortisone, and vitamin B1 is hypothesized to improve outcomes in sepsis through a number of mechanisms. Vitamin C is an important contributor to endothelial integrity and severe deficiency states (e.g. scurvy) can result in endothelial breakdown with resultant vascular leak and edema. In addition, vitamin C is a potent anti-oxidant and is integral to endogenous vasopressor synthesis. Hydrocortisone, a potential adjunctive therapy in septic shock, may act synergistically with vitamin C. Vitamin B1, a key cofactor of pyruvate dehydrogenase, is a critical component of metabolic dysfunction without which a shift towards anaerobic energy production occurs. Vitamin B1 is also a necessary component of the pentose phosphate pathway, which plays a role in reducing oxidative stress. While the physiologic effects of these drugs given in combination is not entirely known, we hypothesize that there will be synergistic effects with respect to the metabolic resuscitation of sepsis.

## **2. TRIAL DESIGN**

### **2.1 Overview**

This will be an investigator-initiated, multicenter, randomized, placebo-controlled, parallel group, double-blind, superiority trial of vitamin C, hydrocortisone, and vitamin B1 vs. placebo in participants with sepsis and septic shock. A total of 200 adult participants will be enrolled. The primary outcome will be the change in SOFA score between enrollment and 72-hours. Key secondary outcomes include the incidence of renal failure during the index ICU stay and survival at 30 days.

### **2.2 Allocation**

Participants will be randomized in a 1:1 ratio to either the combination of vitamin C, hydrocortisone, and vitamin B1 or placebo in blocks with random sizes of 2 or 4. The randomization will be stratified according to site. An independent statistician will create the randomization list using a random number generator. The complete list will only be shared with an independent pharmacy consultant, who will not be involved in clinical care. The pharmacy consultant and the independent statistician will both store the randomization list. The research pharmacy at each enrolling site will receive a site-specific randomization list.

### **2.3 Intervention**

#### **2.3.1 Vitamin C, Hydrocortisone, and Vitamin B1**

The study drugs will consist of vitamin C (1.5g every 6 hours x 4-days), hydrocortisone (50mg every 6 hours x 4-days), and vitamin B1 (100mg every 6 hours x 4-days).

#### **2.3.2 Placebo**

The placebo will consist of matching volumes of normal saline (0.9% NaCl). See below section 4.4 for specifics of drug and placebo preparation.

### **2.4 Blinding**

The trial will be double-blind; participants, investigators, and the clinical team will be blinded to the allocation. Only the pharmacy providing the study drug will be aware of the allocation. The pharmacy will not be involved with clinical care or outcome evaluation.

As vitamin C possess a yellow tinge, the bags containing the vitamin C/placebo will be covered with light-protective bags. In testing, after dilution there is not distinguishing characteristics of the vitamin C vs. placebo in the IV tubing. Vitamin C, hydrocortisone, and vitamin B1 are not known to have distinctive rapid effects which could lead to unblinding.

The decision to unblind will be at the complete discretion of the treating physician and clinical team. If a clinical team wishes to unblind a participant (e.g. if anaphylaxis occurs), they will contact the research pharmacy who will reveal the study group to the clinical team (but the research team will remain blinded). However, we do not expect many scenarios where emergency unblinding will be necessary. In case unblinding occurs, the reason(s) will be clearly documented in the case report form. The patient will no longer receive study medications, but will be followed for outcomes.

### **2.5 Regulatory Issues**

An Investigational New Drug (IND) application was submitted to and approved by the Food and Drug Administration (FDA) for the study of vitamin C, hydrocortisone, and vitamin B1 in sepsis and septic shock (IND # 136882).

The trial has been registered on ClinicalTrials.gov: NCT03389555

### **3. SETTING AND PARTICIPANT POPULATION**

#### **3.1 Setting**

The trial will be conducted at approximately 13 hospitals in the United States. Additional sites might be recruited if needed.

#### **3.2 Inclusion criteria**

Inclusion criteria:

- 1) Adult participant (age  $\geq$  18 years)
- 2) Suspected (cultures drawn and antibiotic given) or confirmed (via culture results) infection
- 3) Receiving (continuous infusion) vasopressor (norepinephrine, phenylephrine, epinephrine, dopamine, angiotensin II, or vasopressin)
  - a. Hypotension related primarily to sepsis as opposed to another cause of hypotension (e.g. bleed, cardiogenic shock)

#### **3.3 Exclusion criteria**

Exclusion criteria:

- 1) Member of a protected population (pregnant, prisoner)
- 2) Known history of kidney stones within the past 1 year (not including incidentally noted stones noted on imaging studies)
- 3) End stage renal disease requiring dialysis (hemodialysis or peritoneal dialysis)
- 4) Known history of G6PD deficiency
- 5) Known history of Hemochromatosis
- 6) Comfort Measures Only status
- 7) Anticipated death within 24-hours despite maximal therapy (as determined by the enrolling physician)
- 8) Receiving supplemental vitamin B1 in a dose greater than that contained in a multivitamin (<2mg)
- 9) Clinical indication for steroids (e.g. chronic use) as determined by the clinical team providing this drug
- 10) Clinical indication for ascorbic acid supplementation in any form
- 11) Clinical indication for vitamin B1 as determined by the clinical team providing this drug
- 12) Known allergy to vitamin C, hydrocortisone, or vitamin B1

Justification of Inclusion and Exclusion Criteria: The inclusion criteria were chosen to isolate a septic participant population with high risk of organ injury and death. The exclusion criteria were chosen to minimize the risk of potential harm and to ensure that participants enrolled do not already have chronic end-stage renal failure with a high likelihood of early need for renal replacement therapy. By evaluating this high-risk population (i.e., most likely to die), we will target those most likely to benefit and therefore increase the probability of showing efficacy.

#### **3.4 Pregnancy**

Hydrocortisone is considered pregnancy class C on the basis of animal studies showing an association between prenatal parenteral hydrocortisone use and risk of cleft-palate. In addition, there are concerns about effects of hydrocortisone on fetal growth and the possibility of neonatal adrenal insufficiency. The effects of high-dose vitamin C and thiamine in pregnancy are not entirely known. As such, participants who are pregnant will be excluded from the study. Prior to enrollment, all participants of potentially child-bearing potential (women aged <45 years) will be required to have a negative serum or urine HCG test (generally performed as standard-of-care).

We will additionally inform all women of child-bearing potential who are randomized in this study that we recommend they remain abstinent or use two forms of birth control during the study period and for a period of 48-hours after the last dose of study drug.

#### **4. TRIAL PROCEDURES**

##### **4.1 Participant Identification**

Screening will be performed in the emergency department and intensive care units (ICUs) with the assistance of electronic screening mechanisms. Detailed screening logs, with reason(s) for exclusion will be kept at each site and reported in the final publication.

We anticipate that all patients, as part of standard-of-care for the septic patient, will have a urine or serum HCG test performed (if a female of child-bearing age). If this test is not sent as part of standard-of-care, it should be sent prior to consent.

##### **4.2 Consent procedures**

Informed, written consent will be obtained for all participants prior to enrollment.

After it is determined that they meet all inclusion criteria and no exclusion criteria, the participant (or legally authorized representative [LAR] if the participant is not able to provide consent) will be approached for written informed consent by a physician co-investigator from the team. The investigator will provide the participant/representative information regarding the background and significance of the study, eligibility criteria, and a description of the protocol. To ensure we are correctly identifying the potential participant's LAR, we communicate with members of the clinical team. The consent process may need to be modified based on site-specific IRB recommendations.

The name of the study investigator obtaining consent will be clearly documented, and this person will sign the informed consent document and provide the date and time of their signature. If a physician is performing remote consent, then a copy of the consent form will be signed as soon as he/she is physically present. Signed copies of the consent form will be given to the participant/surrogate, and the original consent document will be stored in the secure study file. In obtaining and documenting informed consent, each investigator will comply with the applicable regulatory requirements and adhere to the ethical and Good Clinical Practice principles that have their origin in the Declaration of Helsinki.

##### **4.3 Randomization**

After consent is obtained, the research team will notify the local research pharmacy. The research pharmacy will be in possession of the randomization list and will determine which arm (intervention vs. placebo) the participant will be enrolled in.

Patients should be randomized, consented, and enrolled in the study as soon as possible after meeting inclusion criteria. Patients should not be *consented* if it has been >24hours since the patient met inclusion criteria (i.e. start of vasopressors). At the time of randomization and study drug administration, the patient should still be receiving a vasopressor. The patient should not be given study drug if the vasopressor has been stopped (e.g. patient met inclusion criteria overnight but could not be consented for logistical reasons and then improves to the point of no longer requiring a vasopressor). In this scenario, the patient will be entered into the database as consented but not enrolled.

#### **4.4 Drug preparation and administration**

The vitamin C and vitamin B1 will be mixed together in 100ml of normal saline and administered intravenously over 45-60 minutes. The hydrocortisone will be given intravenously as a push-dose in 1ml of saline over 1-2 minutes. The placebo will be given using techniques and volumes matching those of the study medications.

All study medications will be continued for 4-days or until the participant expires or leaves the intensive care unit.

##### *4.4.1 Contingencies and Participant Withdrawal*

- In the unlikely event that a participant is discharged alive from the hospital prior to 4 days after enrollment, all study medications will be stopped. The participant will remain in the study and will be followed for outcomes.
- Hydrocortisone is occasionally used for refractory septic shock. If the clinical team opts to provide a participant hydrocortisone, the hydrocortisone will be given open-label but the vitamin C/B1 will remain randomized and blinded. In this case, the research team will ensure that study hydrocortisone/placebo is replaced by open-label hydrocortisone. The participant will remain in the study and will be followed for outcomes.
- If the clinical team decides to give the participant vitamin B1 for clinical purposes, the study drug will be continued (including thiamine) as long as the total maximum dose of vitamin B1 is  $\leq 1,500\text{mg/day}$ . 1,500mg day is a standard dose for Wernicke's encephalopathy at many institutions and has not been associated with any increased harm.
- If the clinical team decides to give the participant vitamin C for clinical purposes, further administration of study meds will be stopped. The participant will remain in the study and will be followed for outcomes.
- If a participant withdraws from the study, further administration of study meds will be stopped. Data collected prior to withdrawal will be maintained but additional data will not be collected.

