##### *4.5.2 Specimen samples*

At the T1, T2, T3, and T4 time points, blood will be sent for complete blood count (including hemoglobin, white blood cell count, platelet count), a serum chemistry (including sodium, potassium, chloride, bicarbonate, blood urea nitrogen, creatinine, glucose, aspartate transaminase, alanine transaminase, and total bilirubin), and a venous blood gas to measure lactate. These tests will be performed by the clinical laboratory at each site. As many of these laboratory tests are commonly obtained for clinical purposes, these tests do not need to be repeated if a result is available from the clinical care of the participant within 2 hours of the time point (or within 12 hours of the T4 time-point).

In addition to traditional clinical markers, blood will be obtained for future biomarker analysis (including inflammatory biomarkers, markers of endothelial function, and markers of mitochondrial function), and measurement of vitamin C, vitamin B1, and cortisol levels. The total volume of blood that may be drawn for a participant at each time point will not exceed 60mls. Levels of vitamin C, vitamin B1, and cortisol will be measured at time T1 and time T3 only. 20ml of urine will be collected for future biomarker analysis at T1, T2, and T3.

[figure not shown]
If performed as part of standard-of-care, results of urinalysis and urine sediment testing will be collected prior to enrollment.

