##### 5.1.2 Key Secondary Outcomes

Incidence of Acute Renal Failure – Renal failure will be defined as the development of Kidney Disease Improving Global Outcomes [KDIGO] Stage 3 acute kidney injury during the index ICU stay after study enrollment.

KDIGO Stage	Serum creatinine criteria	Urine output criteria
1	Increase in serum creatinine of more than or equal to 0.3 mg/dl ( $\geq$ 26.4 $\mu$ mol/l) or increase to more than or equal to 150% to 200% (1.5- to 2-fold) from baseline	Less than 0.5 ml/kg per hour for more than 6 hours
2	Increase in serum creatinine to more than 200% to 300% (> 2- to 3-fold) from baseline	Less than 0.5 ml/kg per hour for more than 12 hours
3	Increase in serum creatinine to more than 300% (> 3-fold) from baseline (or serum creatinine of more than or equal to 4.0 mg/dl [<math>\geq</math> 354 <math>\mu</math>mol/l]) with an acute increase of at least 0.5 mg/dl [44 <math>\mu</math>mol/l])	Less than 0.3 ml/kg per hour for 24 hours or anuria for 12 hours OR New renal replacement therapy (RRT)

**30-Day Mortality** – Mortality at 30-days. This will be assessed by review of the medical records if the participant remains in the hospital or if the participant expired while in the hospital. If the participant was discharged, 30-day mortality will be assessed by contacting the participant by phone or by searching the National Center for Health Statistics (NCHS) National Death Index (NDI) consistent with a recent multicenter phase III trial in sepsis. Phone calls will be made by the research team at each site.

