### 6.2.3 30-day mortality

Survival until 30 days will be analyzed using survival analysis. Participants lost to follow-up will be censored and the censoring will be assumed non-informative. Results will be presented with Kaplan-Meier curves and the groups compared using the log-rank test. Hazard ratios with 95% confidence intervals will be obtained using Cox's proportional hazards models. The proportional hazards assumption will be verified by visual inspection of the Kaplan-Meier curves and statistically by including a product term (i.e. "interaction") between the treatment group variable and the natural logarithm of time in the model. If the proportional hazards assumption is not met, only the Kaplan-Meier curves and the p-value from the log-rank test will be presented.

Adverse events and other binary outcomes will be presented and analyzed like renal failure.

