## 7. DATA COLLECTION AND MANAGEMENT

### 7.1 Data collection process

Data collection will be the responsibility of the individual site investigators with oversight from the trial coordinating center. Most variables (i.e. demographics, sepsis characteristics and laboratory results) will be obtained prospectively from the electronic medical record. 30-day follow-up regarding safety and mortality end-points will be obtained via telephone call post-discharge (unless the participant remains in the hospital at 30-days). Data will be entered directly into the online database software (see below).

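### The only participant-initiated way to stop is full withdrawal, which ends data collection; no option keeps outcome follow-up, so outcomes may be lost avoidably

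*Protocol*

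**What the plan says.** Protocol section 4.4.1 ends its list of contingencies with withdrawal: "If a participant withdraws from the study, further administration of study meds will be stopped". The next sentence deals with data: "Data collected prior to withdrawal will be maintained but additional data will not be collected". The SAP's section 4.4.1 has the same text.

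Other reasons for stopping drug are treated differently. For discharge from hospital before day 4, and for vitamin C given by the clinical team, section 4.4.1 stops study medication and adds "The participant will remain in the study and will be followed for outcomes". For unblinding, section 2.4 says "The patient will no longer receive study medications, but will be followed for outcomes".

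On data sources, section 7.1 says that most variables "will be obtained prospectively from the electronic medical record". For the scheduled clinical laboratory tests, section 4.5.2 gives a tolerance around the sampling time: "these tests do not need to be repeated if a result is available from the clinical care of the participant within 2 hours". Section 5.1.2 allows 30-day mortality after discharge to be found by telephone or through the National Death Index (NDI).

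On analysis, section 6.2.1 includes everyone who received a first dose. Section 6.2.2 imputes the 72-hour SOFA score for deaths only. Section 6.2.3 says of mortality: "Participants lost to follow-up will be censored and the censoring will be assumed non-informative".

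**The concern.** The protocol accepts in several places that ending study drug need not end follow-up, but does not extend this to a request from the participant or representative. The only listed response to such a request is the one that closes data collection. A site facing someone who objects only to the infusions or the research blood draws has no written alternative, and the 12 or 13 sites may handle such cases differently.

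The primary outcome and both key secondary outcomes are at stake. A participant who withdraws alive before 72 hours may have no final SOFA score, and the plan gives no rule for that case. Renal failure status over the index ICU stay may be incomplete. For mortality, if withdrawal is handled as loss to follow-up, the analysis rests on censoring being unrelated to prognosis. In a population on vasopressors, with consent by a representative allowed (section 4.2), requests to stop could plausibly follow deterioration or recovery. Missingness would then depend on prognosis, and enrolling more participants would not correct the bias.

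**Working it through.** **1. Which stops keep follow-up**

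| Trigger | Study drug | Outcome follow-up | Section |
|---|---|---|---|
| Hospital discharge before day 4 | stops | continues | 4.4.1 |
| Vitamin C given by clinical team | stops | continues | 4.4.1 |
| Unblinding | stops | continues | 2.4 |
| Participant withdraws from the study | stops | ends; earlier data kept | 4.4.1 |
| Participant or representative wants only drug or sampling stopped | not addressed | not addressed | none |

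**2. Whether the loss is avoidable**

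Record review (7.1), laboratory results from clinical care (4.5.2) and an NDI search (5.1.2) need no new procedure or visit. They do need permission, and the two documents contain no step for asking for it.

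**3. The plan's power figures, reproduced**

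Inputs from section 6.1, two-sided alpha 0.05, 100 per arm:

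- SOFA, decrease of 6 (SD 4) against 4 (SD 2), unequal-variance t-test. SE = √(16/100 + 4/100) = 0.447. Noncentrality = 2/0.447 = 4.47 on about 146 df. Power is 99.3% (plan: above 99%).
- Renal failure, 30% against 55%, Fisher's exact test by full enumeration: 93.9% (plan: 94%).
- Mortality, 20% against 40%, Fisher's exact test at 91 per arm: 80.8% (plan: 182 participants for 80%).

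**4. Power if every withdrawn participant is lost**

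No withdrawal rate is given, so 0 to 20% is assumed, equal in both arms, with all three outcomes lost for everyone who withdraws. That overstates the loss, because earlier data are kept. The same calculations at the reduced arm size give:

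| Loss | n per arm | SOFA | Renal failure | Mortality |
|---|---|---|---|---|
| 0% | 100 | 99.3% | 93.9% | 84.4% |
| 5% | 95 | 99.1% | 92.0% | 82.4% |
| 9% | 91 | 98.9% | 90.9% | 80.8% |
| 10% | 90 | 98.8% | 90.8% | 80.2% |
| 15% | 85 | 98.4% | 89.3% | 77.8% |
| 20% | 80 | 97.8% | 86.2% | 74.5% |

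Enrolling 200 against a need of 182 leaves room for 1 − 182/200 = 9% loss.

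**5. Extreme bounds on the mortality difference**

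With u unknowns per 100 in each arm, each arm's mortality can vary over u points, so the risk difference spans 2u points: 10 for u = 5 and 4 for u = 2. The planned difference is 40% − 20% = 20 points.

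Example with u = 5 and the planned rates among those observed: 19/95 against 38/95 deaths, a difference of 20 points, Fisher p = 0.004.

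- All unknown treated participants die and all unknown placebo participants survive: 24/100 against 38/100, 14 points, p = 0.046.
- The reverse: 19/100 against 43/100, 24 points.

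The span is 24 − 14 = 10 points. These are limits under an assumed rate, not predictions. No corresponding bound was computed for SOFA or renal failure.

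**The case against.** A reader might infer that anyone who declines only infusions or blood draws must lose all outcomes. The documents do not say so. The bullet applies to a participant who withdraws from the study; on partial refusal the text is silent. Given how other drug stops are handled, a site could reasonably keep such a person for outcomes. For partial refusal, then, the loss is a risk created by a gap, not a stated rule.

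It can also be said that comparing withdrawal with the other drug stops is unfair, because consent still stands in those cases. That is right for someone who refuses all further data, and ending collection then is proper. It does not explain why nobody is asked which kind of stopping is meant.

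Further points stand. Outcomes recorded before withdrawal are kept, and a withdrawn participant treated as lost to follow-up contributes survival time until censoring. The consent pages are not in the review copy and the CRF is not reproduced, so graded options may exist there. The link to prognosis is plausible but undocumented, and section 4.2 permits consent by a representative without saying how common it will be. The 10-point span follows from any 5% missingness, taken to its extremes. The effect on power is small.

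What remains is the operative text: the one listed participant-initiated route ends data collection, and much of the resulting loss could be prevented by asking for permission.

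**Conclusion.** The concern holds as an avoidable weakness in the design that should be corrected. It is not an error in the plan's figures, all of which reproduce. Outcomes not yet recorded at withdrawal may be lost unnecessarily. If withdrawal relates to prognosis, the comparison among dosed participants and the non-informative censoring assumption could be biased.

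The size of any bias cannot be estimated from the documents. The mortality spans of 10 points (5 unknowns per arm) and 4 points (2 per arm) are extreme bounds at assumed rates. Mortality power stays at about 80% up to roughly 10% loss, and SOFA power is 97.8% even at 20%, so precision is not the reason to act.

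The missing analysis rule for a living participant without a 72-hour SOFA score is a separate gap. Graded withdrawal would make such cases fewer but would not supply the rule.

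**What to change.** Amend the withdrawal bullet in section 4.4.1 of both documents. When a participant or representative asks to stop, the site asks which level applies and the CRF records one:

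- (a) study drug, research samples or both stop, and outcome collection continues;
- (b) no further contact, but record review and vital status, including an NDI search, are permitted;
- (c) no further data of any kind.

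The present sentence on ending data collection would apply only to (c), so the right to withdraw completely is unchanged. Align the consent form if it does not already offer these levels.

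The cost is protocol and, if needed, consent wording, one CRF field if none exists, an IRB amendment and a slightly longer consent conversation. No visits are added.
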